5.3.2.3. Analysis Methods for Primary Estimand

The primary efficacy analysis for study 77242113PSO2002 will be based on the FAS defined in Section 4.2. Since there is no control arm (placebo), in this primary analysis, only the proportion of participants who achieve a PASI75 response and its 95% confidence interval at Week 36 will be summarized for each intervention group.

The data handling method specified in Section 5.3.1.2.3 will be applied. More specifically, participants with ICEs 1-2 before Week 36 will be considered as PASI75 non-responders at Week 36. Participants with ICE 3, observed PASI data after this ICE will be utilized in the analysis. After accounting for the ICEs for the primary estimand, participants with the missing data of the primary endpoint at Week 36 will be considered as non-responders.

5.4. Secondary Endpoints Analysis

5.4.1. Study 77242113PSO2001

5.4.1.1. Multiplicity Adjustment for Testing Procedures

No multiplicity adjustment will be made for the secondary endpoints for study 77242113PSO2001. All statistical testing will be performed at the 2-sided 0.05 significance level. Nominal p-values will be presented.

5.4.1.2. Secondary Endpoint(s)

The secondary objectives are: (a) To characterize additional efficacy of JNJ-77242113 versus placebo, (b) To evaluate the effect of JNJ-77242113 treatment on patient-reported psoriasis severity versus placebo and (c) To evaluate the effect of JNJ-77242113 treatment on dermatology-specific and general health-related quality of life versus placebo in participants with moderate-to-severe plaque psoriasis.

The secondary endpoints to address these objectives are the following:

To characterize additional efficacy of JNJ-77242113 versus placebo

1. Proportion of participants achieving PASI 90 ($\geq 90\%$ improvement from baseline in PASI) at Week 16
2. Proportion of participants achieving PASI 100 (100% improvement from baseline in PASI) at Week 16
3. Proportion of participants achieving an IGA score of cleared (0) or minimal (1) at Week 16
4. Proportion of participants achieving an IGA score of cleared (0) at Week 16
5. Change from baseline in PASI total score at Week 16
6. Change from baseline in BSA at Week 16

To evaluate the effect of JNJ-77242113 treatment on patient-reported psoriasis severity versus placebo

7. Change from baseline in Psoriasis Symptoms and Signs Diary (PSSD) symptoms score at Week 16

8. Change from baseline in PSSD signs score at Week 16
9. Proportion of participants achieving PSSD symptoms score=0 at Week 16 among participants with a baseline symptoms score ≥ 1 .
10. Proportion of participants achieving PSSD signs score=0 at Week 16 among participants with a baseline signs score ≥ 1 .

To evaluate the effect of JNJ-77242113 treatment on dermatology-specific and general health-related quality of life versus placebo

11. Proportion of participants achieving a DLQI of 0 or 1 at Week 16 among participants with baseline DLQI score > 1
12. Change from baseline in domain scores of the Patient-Reported Outcomes Measurement Information System (PROMIS-29) at Week 16
13. Proportion of participants who achieve at least a 5-point improvement from baseline in each PROMIS-29 domain at Week 16

5.4.1.2.1. Definition of Endpoint(s)

5.4.1.2.1.1. Psoriasis Area and Severity Index (PASI)

Details refer to section [5.3.1.1](#).

5.4.1.2.1.2. Investigator's Global Assessment (IGA)

The IGA documents the investigator's assessment of the participant's psoriasis at a given time point. Overall lesions are graded for induration, erythema, and scaling. The participant's psoriasis is assessed as cleared (0), minimal (1), mild (2), moderate (3), or severe (4).

5.4.1.2.1.3. Body Surface Area (BSA)

Body Surface Area is a commonly used measure of severity of skin disease. It is defined as the percentage of surface area of the body involved with the condition being assessed, (ie, plaque psoriasis). The handprint method for assessing BSA will be used in this study, where the surface area of the patient's hand including the palm and all five digits is used as a guide to estimate 1% BSA.

5.4.1.2.1.4. Psoriasis Symptom and Sign Diary (PSSD)

The PSSD includes PRO questionnaires designed to measure the severity of psoriasis symptoms and signs for the assessment of treatment benefit. This study uses a 7-day recall version of the PSSD that asks the participant to answer the questions thinking about the last 7 days. The PSSD is a self-administered PRO instrument and includes 11 items covering symptoms (itch, pain, stinging, burning, and skin tightness) and patient-observable signs (skin dryness, cracking, scaling, shedding or flaking, redness, and bleeding) using 0 to 10 numerical rating scales for severity. Two

sub-scores are derived each ranging from 0 to 100: the psoriasis symptom score and the psoriasis sign score. A higher score indicates more severe disease.

The calculations of PSSD symptom, and sign scores are listed below:

Symptom Score (0-100)

- a. Symptom score includes **itch** (Q1), **pain** (Q11), **stinging** (Q10), **burning** (Q9) and **skin tightness** (Q4).
- b. Averaging items on 7 days recall symptom scores when at least 3 items ($\geq 50\%$ of 5 items) on this scale are answered. Then, the average value is converted into 0-100 scoring such that Symptom score = average value x 10 with 0 representing the least severe and 100 the most severe.

Sign Score (0-100)

- a. Sign score includes **skin dryness** (Q2), **cracking** (Q3), **scaling** (Q5), **shedding or flaking** (Q6), **redness** (Q7) and **bleeding** (Q8).
- b. Averaging items on 7 days recall sign scores when at least 3 items ($\geq 50\%$ of 6 items) on this scale are answered. Then, the average value is converted into 0-100 scoring such that Sign score = average value x 10 with 0 representing the least severe and 100 the most severe.

5.4.1.2.1.5. Dermatological Life Quality Index (DLQI)

The DLQI is a dermatology-specific health-related quality of life (HRQoL) instrument designed to assess the impact of the disease on a participant's HRQoL. It is a 10-item questionnaire that assesses HRQoL over the past week and in addition to evaluating overall HRQoL, can be used to assess 6 different aspects that may affect quality of life: symptoms and feelings, daily activities, leisure, work or school performance, personal relationships, and treatment. The total score ranges from 0 to 30 with a higher score indicating greater impact on QoL

For a partially answered questionnaire (eg, not all 10 answers in the DLQI questionnaire were available):

- If one question's answer is not available, this question will be scored 0. The total score will then be calculated.
- If two or more questions' answers are unavailable, the questionnaire is not scored. Hence, the total score and each of the 6 component scores will be set to missing.
- If one question from one of the 6 component scores is missing, the affected component score will be set to be missing.

5.4.1.2.1.6. Patient-Reported Outcomes Measurement Information System-29 (PROMIS-29)

The PROMIS-29 is a 29-item generic HRQoL survey, assessing each of the 7 PROMIS domains (depression; anxiety; physical function; pain interference; fatigue; sleep disturbance; and ability to

participate in social roles and activities) with 4 questions. The questions are ranked on a 5-point Likert Scale. There is also one 11-point rating scale for pain intensity.

The raw score of each domain is converted into a standardized score with a mean of 50 and a standard deviation (SD) of 10 (T-Score). The standardized T-score is reported as the final score for each participant. Pain Intensity is presented as raw responses (0-10). For PROMIS domains of Depression, Anxiety, Physical Function, Pain Interference, Fatigue, a score of 50 is the average for the United States general population with a standard deviation of 10, because testing was performed on a large sample of the general population. However, the other two domains (Ability to Participate in Social Roles and Activities and Sleep Disturbance) were not centered in a national sample. For these two domains, a score of 50 represents the average of the calibration sample which was generally more enriched for chronic illness, and a score of 50 likely represents somewhat sicker people than the general population. A higher PROMIS T-score represents more of the concept being measured. For negatively-worded concepts like Anxiety, a T-score of 60 is one SD worse than average. By comparison, an Anxiety T-score of 40 is one SD better than average. However, for positively-worded concepts like Physical Function, a T-score of 60 is better than average while a T-score of 40 is better. Participants will undergo this assessment at time points according to the SoA.

5.4.1.2.2. Main Estimands for Secondary Endpoints

The secondary endpoints will be analyzed similarly as the primary estimand described in section 5.3.1.2.1 as the main estimand. The main estimand will be considered for both binary and continuous secondary endpoints. The analysis strategy for ICEs and missing data will be handled in the same manner as the primary estimand for the primary endpoint

- ICEs 1-2: Composite strategy
- ICE 3: Treatment policy strategy

The study intervention and population are the same as the primary estimand.

BINARY ENDPOINTS

Variables and Population-level Summary: Difference in the proportions of participants achieving a clinical response (eg, PASI 90 responses at Week 16) between the treatment groups. The variables and population level summaries for the other secondary binary endpoints are similarly described.

CONTINUOUS ENDPOINTS

Variable (Endpoint): change from baseline to Week 16 (change = Week 16 - baseline).

- Participants who have intercurrent events in categories 1, 2 through Week 16 will have a zero change from baseline assigned from the point of the ICE, regardless of the observed data.

Population-level summary: LSMean difference in change from baseline in eg, change from baseline in total PASI score at Week 16 between JNJ-77242113 treatment groups and the placebo group. The variables and population -level summaries for the other secondary continuous endpoints are similarly described.

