10.6.1. Adverse Event Definitions and Classifications

Adverse Event

An AE is any untoward medical occurrence in a clinical study participant administered a pharmaceutical (investigational or non-investigational) product. An AE does not necessarily have a causal relationship with the intervention. An AE can therefore be any unfavorable and unintended sign (including an abnormal finding), symptom, or disease temporally associated with the use of a medicinal (investigational or non-investigational) product, whether or not related to that medicinal (investigational or non-investigational) product. (Definition per International Council for Harmonisation [ICH]).

This includes any occurrence that is new in onset or aggravated in severity or frequency from the baseline condition, or abnormal results of diagnostic procedures, including laboratory test abnormalities.

Note: The sponsor collects AEs starting with the signing of the ICF (refer to Section [8.3.1](#), for time of last AE recording).

Serious Adverse Event

An SAE based on ICH and EU Guidelines on Pharmacovigilance for Medicinal Products for Human Use is any untoward medical occurrence that at any dose:

- Results in death
- Is life-threatening
(The participant was at risk of death at the time of the event. It does not refer to an event that hypothetically might have caused death if it were more severe.)
- Requires inpatient hospitalization or prolongation of existing hospitalization
- Results in persistent or significant disability/incapacity
- Is a congenital anomaly/birth defect
- Is a suspected transmission of any infectious agent via a medicinal product
- Is Medically Important*

*Medical and scientific judgment should be exercised in deciding whether expedited reporting is also appropriate in other situations, such as important medical events that may not be immediately life-threatening or result in death or hospitalization but may jeopardize the participant or may require intervention to prevent one of the other outcomes listed in the definition above. These should usually be considered serious.

If a serious and unexpected AE occurs for which there is evidence suggesting a causal relationship between the study intervention and the event (eg, death from anaphylaxis), the event must be

reported as a serious and unexpected suspected adverse reaction even if it is a component of the study endpoint.

Unlisted (Unexpected) Adverse Event/Reference Safety Information

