5.3. Primary Endpoint Analysis

5.3.1. Study 77242113PSO2001

5.3.1.1. Definition of Primary Endpoints

The primary efficacy endpoint is the proportion of participants achieving PASI 75 response at Week 16, defined as at least a 75% reduction from baseline in PASI total score.

The PASI is a system used for assessing and grading the severity of psoriatic lesions and their response to therapy. In the PASI system, the body is divided into 4 regions: the head, trunk, upper extremities, and lower extremities which account for 10%, 30%, 20%, and 40% of the total BSA, respectively. Each of these areas is assessed separately for erythema, induration, and scaling, which are each rated on a scale of 0 to 4; and the area of involvement for psoriatic lesion is rated on a scale of 0 (no involvement) to 6 (90% to 100% involvement). The PASI produces a numeric score that can range from 0 (no psoriasis) to 72. A higher score indicates more severe disease.

Efficacy endpoints related to the PASI score are defined below:

PASI 50 Responders

Participants with $\geq 50\%$ improvement in PASI from baseline will be considered PASI 50 responders.

PASI 75 Responders

Participants with $\geq 75\%$ improvement in PASI from baseline will be considered PASI 75 responders.

PASI 90 Responders

Participants with $\geq 90\%$ improvement in PASI from baseline will be considered PASI 90 responders.

PASI 100 Responders

Participants with a PASI score of 0 will be considered PASI 100 responders.

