5.3.1.2.1. Primary Estimand (Estimand 1)

The primary estimand, based on the above primary objective, is defined by the following 5 attributes which assess the treatment effects not only based on the variable measurements, but also based on intercurrent events:

Study intervention:

- JNJ77242113 25 mg QD, 50 mg QD, 25 mg BID, 100 mg QD, and 100 mg BID.
- Placebo

Population: adult participants with moderate to severe psoriasis

Variable/endpoint: Binary response variable, where a responder is defined as a participant achieving a PASI75 response at Week 16. A participant with an intercurrent event in categories 1-2 defined below will be considered as a non-responder.

Intercurrent Events (ICEs) and their corresponding strategies.

ICEs	Analysis Strategy for Addressing Intercurrent Events
1. Discontinuation of study intervention due to lack of efficacy, or an AE of worsening of psoriasis prior to Week 16	Composite Strategy: Participants with these intercurrent event are considered as non-responders. The occurrence of these intercurrent events is captured in the variable definition.

2. Initiation of a protocol-prohibited medication or therapy during the study that could improve psoriasis prior to Week 16	
3. Discontinuation of study intervention for reasons other than ICE 1	Treatment Policy: observed data will be used regardless of whether or not this intercurrent event had occurred.

- ICEs 1 and 2 will be handled by the composite strategy, where the occurrence of the ICE will be incorporated into the variable definition. Participants experiencing ICE 1 or 2 will be considered not to have achieved the primary endpoint.

- ICE 3 will be handled using the treatment policy strategy regardless of the intercurrent event.

Note: For participants experiencing multiple ICEs, ICE 2 will override ICE 3.

A list of Participants who experienced ICEs 1-3 will be provided.

Population level summary: Difference in the proportions of participants achieving a PASI 75 responses at Week 16 between the treatment groups.

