5.4.1.2.3. Supplementary Estimands

The supplementary estimands defined in Section 5.3.1.2.2.1 (Hypothetical Strategy) and Section 5.3.1.2.2.2 (Treatment Policy Strategy) for the primary endpoint will also be used for selected binary secondary endpoints:

- Proportion of participants achieving PASI 90 ($\geq 90\%$ improvement from baseline in PASI) at Week 16
- Proportion of participants achieving PASI 100 (100% improvement from baseline in PASI) at Week 16
- Proportion of participants achieving an IGA score of cleared (0) or minimal (1) at Week 16
- Proportion of participants achieving an IGA score of cleared (0) at Week 16

The following table provides the list of variables, summary measure (population-level summary) and intercurrent event strategy for secondary endpoints.

Secondary Endpoint	Variable	Summary Measure (Population-level summary)	Intercurrent Event Strategy
1	Binary response variable, where a responder is defined as a participant achieving a PASI 90 response at Week 16	Difference in the proportions of participants achieving a PASI 90 response at Week 16 between JNJ-77242113 treatment groups and placebo group.	Same analysis strategies as the primary estimand as specified in section 5.3.1.2.1 and two supplementary estimands specified in section 5.3.1.2.2.
2	Binary response variable, where a responder is defined as a participant achieving a PASI 100 response at Week 16	Difference in the proportions of participants achieving a PASI 100 response at Week 16 between JNJ-77242113 treatment groups and placebo group.	Same analysis strategies as the primary estimand as specified in section 5.3.1.2.1 and two supplementary estimands specified in section 5.3.1.2.2.
3	Binary response variable, where a responder is defined as a participant achieving an IGA scores of cleared (0) or minimal (1) at Week 16	Difference in the proportions of participants achieving an IGA score of cleared (0) or minimal (1) at Week 16 between JNJ-77242113 treatment groups and placebo group.	Same analysis strategies as the primary estimand as specified in section 5.3.1.2.1 and two supplementary estimands specified in section 5.3.1.2.2.

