5.4.1.3.2. Continuous Endpoints

Unless otherwise specified, the analyses for continuous secondary endpoints at Week 16 will be based on the following strategies to handle ICEs and missing data.

- ICEs in categories 1 - 2 in the primary estimand (definitions in Section 5.3.1.2.1) will be handled with the Composite Strategy. Participants experiencing ICEs 1-2 will have a zero change (or zero improvement) from baseline assigned from that point onward.
- ICEs in categories 3 in the primary estimand (definitions in Section 5.3.1.2.1) will be handled by the Treatment Policy strategy. The analysis will be performed using observed data regardless of intercurrent events. For participants experiencing multiple ICEs, an ICE in categories 2 of the primary estimand will override an ICE in category 3.
- Missing data will not be imputed after applying the rules for intercurrent events.

To account for the missing data for continuous endpoints of change (or percent change) from baseline measured at more than one post-baseline visit, a MMRM will be used. In MMRM, missing data will not be imputed, but rather missing data will be accounted for through correlation of repeated measures in the model.

Treatment comparisons for the secondary continuous endpoints at Week 16 will also be performed using a Mixed-Effect Model Repeated Measure (MMRM) model under the assumption of missing at random (MAR) with intervention group, visit, baseline weight category (≤ 90 kg, > 90 kg), baseline value for the efficacy endpoint, treatment by visit, baseline weight category by visit and baseline value by visit interaction as explanatory factors, if appropriate. An unrestricted (UN)

variance-covariance matrix for repeated measures within a participant will be used. If the model with unstructured covariance structure does not converge, alternative covariance structures will be tried in the following order, with the first structure that converges being used in the analysis: heterogeneous Toeplitz, standard Toeplitz, and autoregressive of order 1.

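### The zero-change rule for continuous endpoints scores an ICE 1 participant who is worse than baseline better than observed, and no supplementary analysis tests it

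*SAP*

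**What the plan says.** SAP 5.4.1.2.2 applies a composite strategy to ICEs 1 and 2 for binary and continuous secondary endpoints alike. For a continuous endpoint, a participant with either event "will have a zero change from baseline assigned from the point of the ICE, regardless of the observed data". SAP 5.4.1.3.2 restates this: "Participants experiencing ICEs 1-2 will have a zero change (or zero improvement) from baseline assigned from that point onward". SAP 5.4.2.2.3 repeats the rule for the extension study, and SAP 5.5.1.2.1 sends the Week 16 exploratory endpoints to the same strategy.

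SAP 5.3.1.2.1 defines ICE 1 as "Discontinuation of study intervention due to lack of efficacy, or an AE of worsening of psoriasis prior to Week 16". ICE 2 is starting a prohibited therapy that could improve psoriasis. ICE 3 is stopping for any other reason, and there the observed data are kept.

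Change is the visit value minus baseline. For PASI, "A higher score indicates more severe disease" (SAP 5.3.1.1), so a positive change is a worsening.

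On gaps that remain after these rules, SAP 5.4.1.3.2 says: "In MMRM, missing data will not be imputed, but rather missing data will be accounted for through correlation of repeated measures in the model". The hypothetical and treatment-policy estimands defined "for the primary endpoint will also be used for selected binary secondary endpoints" (SAP 5.4.1.2.3). The four chosen are PASI 90, PASI 100, IGA 0 or 1, and IGA 0. No continuous endpoint is among them.

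**The concern.** In the primary estimand, the composite strategy turns ICE 1 or 2 into the unfavourable outcome, non-response. Under the same label, the continuous rule can do the reverse. Part of ICE 1 is stopping for a worsening adverse event. Protocol 10.6.1 says of adverse events: "This includes any occurrence that is new in onset or aggravated in severity or frequency from the baseline condition". For that part of ICE 1, a score above baseline is therefore the expected case, yet zero change replaces it even where a worse value was recorded.

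Two consequences follow for such a participant. The score is better than that of someone with the same course who stayed on treatment or stopped under ICE 3, whose worsening is kept. And because values before the event stay in the model, the profile steps from a positive change to zero at the moment of failure. By-visit least-squares means are planned (SAP 5.5.1.2.2), so that step enters the displayed time course.

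**Working it through.** The plan states no figure for this rule, so there is nothing to reproduce. The documents give 40 participants per arm, the change definition and the rule. They give no ICE rate, no size of worsening and no standard deviation, so every PASI value and count below is an assumption chosen to show the range.

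**One participant.** Assigned minus observed = 0 − (visit value − baseline). A negative result means the rule flatters.

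| Baseline | Observed | Observed change | Assigned | Assigned − observed |
|---|---|---|---|---|
| 20 | 26 | +6 | 0 | −6 (flattered) |
| 20 | 20 | 0 | 0 | 0 |
| 20 | 16 | −4 | 0 | +4 (penalised) |

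In the first row, if +6 was recorded before stopping, the profile in the model runs from +6 to 0, an apparent 6-point improvement caused by the event itself.

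**Arm mean.** As a simple mean (not the MMRM estimate), shift = −(sum of the observed changes that are overridden) / 40.
- 2 participants, each +4: −8/40 = −0.2.
- 8 participants, each +6: −48/40 = −1.2.
- 8 participants, four at +6 and four at −6: −(24 − 24)/40 = 0.
- 8 participants, two at +6 and six at −4: −(12 − 24)/40 = +0.3.

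The sign depends on the mix of worsened and partly improved participants.

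**Active minus placebo.** The shift in the difference is the active-arm shift minus the placebo-arm shift, with every affected participant at +6.
- 1 active, 8 placebo: −6/40 + 48/40 = +1.05, a smaller drug effect.
- 4 active, 4 placebo: 0.
- 4 active, 1 placebo: −24/40 + 6/40 = −0.45, a larger drug effect.

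**When a post-event value exists.** Under Protocol 7.1, participants who stop treatment but stay in the study return for about 4 weeks after the last dose. Someone who stops at Week 6 is followed to about Week 10. A Week 8 value is likely, but Week 12 and Week 16 values usually are not. At Week 16, recorded data are overridden mainly for those who stop from about Week 12 on. For earlier stoppers, zero replaces whatever the MMRM would have implied under missing at random, and the documents do not allow that value to be computed.

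**The case against.** The strongest reply is that zero change is a deliberate and often harsh composite value. Stopping for lack of efficacy does not require worsening, so a partial improver who stops at −4 loses 4 points. For ICE 2, zero usually strips out the benefit of the prohibited therapy. For early stoppers there is often no Week 16 value to override, and the model's implied value could be more favourable than zero in an arm that improves on average. The affected endpoints are secondary or exploratory with nominal p-values, and participants with ICEs will be listed.

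All of this stands, and it limits the point. A reader might infer that the rule generally favours failures, or that it biases the comparison with placebo in a known direction. The documents support neither, because they give no ICE rate and no split between worsened and partly improved participants. Nor does a worsening adverse event show that nail, sleep or social-role scores also worsened.

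The reply does not remove the narrower fact. Where a value worse than baseline has been recorded after ICE 1, the rule replaces it with a better one, and nothing planned shows how much this matters.

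**Conclusion.** The point holds for ICE 1 participants whose score is worse than baseline, on continuous secondary and exploratory endpoints, in both the main study and the extension. For each one, the rule's gain equals the full observed worsening, 6 PASI points in the illustration. The arm-level effect cannot be computed. The assumed scenarios run from −1.2 to +0.3 points in an arm mean and from −0.45 to +1.05 in a treatment difference, and both ranges include zero.

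A reader might take this as a threat to the trial's main conclusion. It is not. Study success rests on the PASI 75 dose-response test, and participants with ICE 1 or 2 are non-responders there and on every binary endpoint. This is a modest defect in the secondary analyses that is cheap to correct.

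**What to change.** In SAP 5.4.1.2.2, 5.4.1.3.2 and 5.4.2.2.3:
- **ICE 1:** at each visit with a value observed after the event, assign the worse of zero and the observed change. Keep zero where no value exists.
- **ICE 2:** keep zero. State which rule governs when a participant has both ICE 1 and ICE 2; the present precedence note covers only ICE 2 over ICE 3.
- **Direction:** define worse for each scale. Higher is worse for PASI, BSA and PSSD. PROMIS-29 domains differ: a higher score is worse for anxiety and better for physical function (SAP 5.4.1.2.1.6).
- **Supplementary analysis:** add a treatment-policy analysis of change in PASI, BSA, PSSD and PROMIS-29, keeping observed values after ICEs 1 and 2, as is already planned for four binary secondary endpoints.

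Carrying the last value forward to Week 16 is not advised. It would treat a possibly transient flare as permanent. Keeping zero at unobserved visits means some apparent recovery remains for early stoppers, and the supplementary analysis should be read alongside for that reason.

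The cost is a short SAP edit, some programming and slightly larger variance. If worsened failures fall mainly on placebo, the estimated drug effect will be somewhat larger than under the present rule, and the SAP should say so.
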